4 SELECTION AND WITHDRAWAL OF SUBJECTS

4.1 Inclusion Criteria

Subjects who meet all of the following criteria will be eligible to participate in the study:

- 1. Age 18-75 years
- 2. Major trauma defined as:
 - a. thoracic and/or abdominal and/or pelvic injury
 - b. necessitating admission to ICU with ventilation anticipated for at least 24 hrs
 - c. hemorrhagic shock defined as systolic blood pressure (SBP) <90 mmHG requiring blood transfusion or base deficit of at least 6 mEq/L pre-hospital arrival or within one hour after hospital arrival
- 3. IRB/IEC-approved consent obtained within 48 hours of first hospital arrival time (i.e., in case of transfers, use time of arrival to first hospital immediately post injury)

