6.2.9 Trauma Related Injury Severity Score (TRISS)

A Trauma Related Injury Severity Score (TRISS) will be recorded (see Appendix 3: TRISS Method). See the Study Reference Manual for details.

The TRISS is a scoring system that assesses probability of survival by looking at the following:

- Injury Severity Score (ISS) looks at head and neck, face, chest, abdomen and pelvic contents, extremity and pelvic girdle, and external injuries and each body region is given a score based on the Abbreviated Injury Score Code (AIS)
- Revised Trauma Score (RTS) also looks at Systolic blood pressure (SBP), Respiratory rate (RR), and GCS
- Age

Confidential Page 37 of 64

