10.2.4.1 Primary Efficacy Analyses

There are two co-primary efficacy endpoints defined in this study:

- CPAx total score at Day 10 (or at hospital discharge, whichever occurs first)
- Organ dysfunction total TTR until Day 28

Both primary endpoints will be compared across treatment groups and tested at the 0.05 level of significance and, by convention, both endpoints must demonstrate statistical significance (i.e., $p \le 0.05$) to conclude treatment superiority for regulatory purposes.

For the first primary efficacy endpoint, CPAx total score at Day 10 (or at hospital discharge, whichever occurs first), the following hypothesis will be tested:

$$H_0$$
: $\mu_{Tp} = \mu_p \ v. s. H_a$: $\mu_{Tp} \neq \mu_p$

Where μ_{Tp} , μ_p denote the CPAx total score at Day 10 (or at hospital discharge, whichever occurs first) in the pooled treatment group (FDY-5301 1 mg/kg and FDY-5301 2 mg/kg combined) and placebo groups, respectively. As the primary analysis, the treatment comparison of the CPAx total scores will be performed using analysis of covariance (ANCOVA). The model will include CPAx total score at Day 10 (or at hospital discharge, whichever occurs first) as dependent variable treatment and stratification category (with or without presence of pelvic or lower limb fractures) as factors; and "baseline" CPAx (the first available datapoint) as a continuous covariate.

The p-values, least-squares means, standard errors, and the 2-tailed 95% confidence intervals for the treatment groups and placebo group will be presented.

Confidential Page 47 of 64

If the difference between the means of the pooled treatment group compared to the placebo group is statistically significant, a step-down procedure will be followed to test the individual FDY-5301 doses compared to placebo. The following testing order of doses will be used:

- 1) FDY-5301 2 mg/kg versus placebo
- 2) FDY-5301 1 mg/kg versus placebo

The same statistical method as for the comparison between the pooled treatment group and placebo will be used.

For the second primary efficacy endpoint, organ dysfunction total TTR, the time will be calculated as date of recovery minus date of treatment start plus 1 day. The time to recovery will be estimated using Kaplan-Meier methodology. The Kaplan-Meier curves will be plotted and the time to recovery will be compared using log-rank test at significance level 0.05. The pooled versus placebo and then step-down analysis procedure will be used.

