10.2.7 Sample Size Determination and Power Calculations

Approximately 252 subjects will be randomized in a 1:1:1 ratio to receive either FDY-5301 1 mg/kg, FDY-5301 2 mg/kg, or placebo (i.e. 84 subjects per group).

With 252 subjects (with a drop-out rate of 15%, corresponding to 213 evaluable subjects), using a 2-sided significance level of 0.05 and placebo group mean in CPAx total score at Day 10 of 30, assuming a standard deviation of 12 (Corner 2015 and Raymond 2020), this would provide >90% power if there exists an improvement of 6 points in the CPAx total score in the pooled treatment group (either FDY-5301 1mg/kg or 2 mg/kg) compared with placebo group, (i.e. scores of 36 for FDY-5301 vs. 30 Placebo).

Given the assumption that median expected organ dysfunction recovery time is 7 days for the placebo group and the median expected organ dysfunction recovery time is 4.9 days for the pooled treatment group (Xiao 2011), i.e. an expected relative risk reduction of 30% and a 2-sided log-rank test at a significance level of 0.05, the study would have approximately 70% power if at least 213 events are observed (based on no subject being censored until Day 28).

Confidential Page 49 of 64

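### The CPAx ANCOVA leaves out injury severity (ISS) and age, which are collected for every subject; prespecifying them would be a cheap gain in precision, though the planned model is not wrong

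*Combined protocol and SAP*

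**What the plan says.** Section 10.2.4.1, like the synopsis, gives the CPAx model in full: Day 10 (or discharge) CPAx as outcome, treatment and fracture stratum as factors, and "CPAx (the first available datapoint) as a continuous covariate". The dose-level tests use the same method. Section 10.2.4.2 gives MRC-SS and worst SOFA a similar ANCOVA, and TTR and survival a log-rank test with no covariate stated.

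Section 6.2.9 says "A Trauma Related Injury Severity Score (TRISS) will be recorded" and describes its parts as ISS, RTS and age. Table 1 schedules it on Day 1 at all sites. Birth date is recorded separately (Section 6.2.1). No efficacy analysis in Section 10.2.4 names any of these. Randomization is stratified by fracture only (Section 7.2).

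Eligibility requires injury "necessitating admission to ICU with ventilation anticipated for at least 24 hrs" (Section 4.1). The first dose may come up to 48 hours after arrival, and the Day 1 window is 24 hours either side of that dose (Table 1).

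**The concern.** An ANCOVA gains precision only from covariates that predict the outcome. Beyond the stratum, the one covariate here is the first CPAx on record. Most CPAx items concern cough, bed mobility, sitting, standing, transfers, stepping and grip (Section 6.1.5). In patients expected to be ventilated, early scores are likely to be compressed at low values and so may predict little. The first available score may also be post-dose, or later than Day 1 if that assessment is missed.

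ISS and age describe the injury and the person, so dosing cannot change them, and they are plausible predictors of function at Day 10. Section 1.4 itself notes the potential heterogeneity of this population, and the randomization does not balance severity or age. What is at stake is interval width, mainly in the dose-level tests, where each comparison loses half of the pooled active group. Chance imbalance in severity would also go unadjusted.

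**Working it through.** **Inputs.** Section 10.2.7 gives the significance level and placebo mean ("using a 2-sided significance level of 0.05 and placebo group mean in CPAx total score at Day 10 of 30"), the effect ("improvement of 6 points in the CPAx total score in the pooled treatment group") and the spread ("assuming a standard deviation of 12"). It also gives 1:1:1 allocation of 252 subjects, with 213 evaluable after 15% drop-out. That is 71 per arm, so 142 pooled active versus 71 placebo.

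**The plan's own figure.** SE = 12 × √(1/142 + 1/71) = 1.744. Power = Φ(6/1.744 − 1.96) = 93.1%, or 92.8% with the noncentral t. The stated figure of more than 90% is confirmed.

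**One dose versus placebo.** SE = 12 × √(1/71 + 1/71) = 2.014. Power = Φ(6/2.014 − 1.96) = 84.6%. This assumes that the 6-point effect, which the plan states for the pooled group, also holds for the single dose. It is the power of that comparison alone.

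**TTR.** With 213 events, a ratio of 4.9/7 = 0.70 and 1/3 on placebo, power = Φ(√(213 × 1/3 × 2/3) × |ln 0.70| − 1.96) = 68.9%, against a stated 70% or so.

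**Adding ISS and age.** Let R² be the share of Day 10 CPAx variance that they explain beyond fracture stratum and first CPAx. Residual SD = 12 × √(1 − R²). The documents give no R², so it is varied. SD 12 is taken as the residual SD of the planned model. Joint power is pooled CPAx power × 68.9%, assuming independence for illustration.

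| Assumed R² | Residual SD | SE, pooled | Pooled power | 2 mg/kg vs placebo | Both co-primaries |
|---|---|---|---|---|---|
| 0 | 12.00 | 1.744 | 93.1% | 84.6% | 64.1% |
| 0.02 | 11.88 | 1.727 | 93.5% | 85.3% | 64.5% |
| 0.05 | 11.70 | 1.700 | 94.2% | 86.4% | 64.9% |
| 0.10 | 11.38 | 1.655 | 95.2% | 88.1% | 65.6% |
| 0.20 | 10.73 | 1.560 | 97.0% | 91.5% | 66.9% |

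The equivalent gain in sample size is 1/(1 − R²): about 2, 5, 11 and 25% more subjects at R² of 0.02, 0.05, 0.10 and 0.20.

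**If SD 12 is the raw SD.** Suppose the existing covariates already explain 10% of the variance. Pooled power then starts at 95.2%, and a further 10% takes it to 96.9%. The gain is 1.7 points, against 2.1 in the table.

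**Cost in degrees of freedom.** The pooled model has 213 − 4 = 209 residual degrees of freedom, and two covariates leave 207. Break-even R² is roughly 2/209, or about 1%.

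**The case against.** The case against is substantial. The planned ANCOVA is prespecified, adjusts for the stratification factor and is valid under randomization; chance imbalance in severity does not invalidate it. Its power is already above 90%, and TTR is what limits success on both co-primaries. All of that stands.

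A reader might infer that precision is certainly being lost. The documents do not support this. They give no correlation between severity and Day 10 CPAx, and at an R² near zero nothing is lost. There are reasons for caution about a large R². Section 6.2.9 says "The TRISS is a scoring system that assesses probability of survival by looking at the following", so the score is built for survival and not function. Eligibility narrows the range of severity, and the fracture stratum already carries part of the extremity and pelvic component.

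A reader might also infer that first CPAx scores sit at the floor. No distribution is given. Ventilation is only anticipated, and a Day 1 score could be taken up to 48 + 24 = 72 hours after arrival. Low compression is a fair inference and no more.

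Nor can it be said that no model anywhere will use these variables. Exploratory covariates are unlisted (Section 10.2.4.3), and Section 10 defers detail to a separate SAP that is not in the file reviewed.

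Finally, entering the whole TRISS is less safe than it looks. RTS uses blood pressure, respiratory rate and GCS. Table 1 allows the score within 24 hours either side of the first dose, and Section 6.2.9 does not fix arrival values, so RTS is not shown to be pre-dose. It may also be hard to score in intubated subjects, and one ANCOVA cannot use different covariates for different subjects. This does not affect ISS and age.

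**Conclusion.** The point holds as an inexpensive improvement. ISS and age are available for everyone and are not in the stated CPAx model. Over the assumed R² range of 2 to 20%, pooled power rises by about 0.4 to 4 points. The 2 mg/kg comparison, if its effect is also 6 points, rises by about 2 to 7 points at R² of 5 to 20%. Joint co-primary power rises by less than 3 points. Confidence is high on the omission and low on the size of the gain, because R² is an assumption. The documents do not support reading this as a flaw in the primary analysis or a shortfall in CPAx power.

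**What to change.** Before unblinding, prespecify ISS and continuous age as covariates in the pooled and dose-level CPAx ANCOVAs, keeping fracture stratum and baseline CPAx.

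- Take age from birth date and not from the TRISS bands, which Appendix 3 cuts at 55 years.
- Use one covariate set for all subjects.
- Fill isolated missing baseline values by simple imputation blind to treatment, so that nobody is dropped.
- Leave RTS out of the primary model unless it is fixed at arrival, pre-dose values and can be scored in every subject.

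The cost is 2 of about 209 degrees of freedom and no new data. Because the protocol itself states the model, the synopsis and Section 10.2.4.1 need rewording as well as the SAP, and Section 12.1 requires IRB/IEC approval of amendments.

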Test Product, Dosage and	 10. Body weight (BW) >140 kg (or >309 lb) 11. History or presence of debilitating neurologic or other neuromuscular disease (e.g., spina bifida, amyotrophic lateral sclerosis, multiple sclerosis) at time of randomization 12. Current metastatic cancer 13. Solid organ transplant recipient 14. Evidence of pre-existing sarcopenia defined as having a pre-trauma Clinical Frailty Score (CFS) of ≥5 or based on clinical judgement (e.g. frail by appearance, cachexia, etc.) 15. Use of systemic corticosteroids, immunomodulators, or oncologic chemotherapy within 6 months of randomization (inhaled and topical steroids are allowed) 16. Use of investigational drugs or devices within 30 days of randomization 17. Any clinically significant abnormality identified prior to randomization that in the judgment of the Investigator or Sponsor would preclude safe completion of the study, or confound the anticipated benefit of FDY-5301 FDY-5301 (dose of 1 mg/kg or 2 mg/kg) will be
Mode of Administration:	administered IV by bolus injection daily for up to 7 injections.
Control Product, Dosage and Mode of Administration:	Placebo (normal saline) will be administered IV by bolus injection daily for up to 7 injections. Placebo will be volume-matched and indistinguishable from FDY-5301.
Duration of Study:	Each subject's participation will be approximately 6 months from the time of screening to study exit.
Statistical Methods:	A stratified randomization scheme will be employed in this study, with presence of pelvic or lower limb fractures as the stratification factor.
	Subjects will be stratified into two groups:
	subjects with pelvic or lower limb fractures
	 subjects without pelvic or lower limb fractures
	Safety Analyses:
	All safety measures will be summarized descriptively. AEs will be summarized by Medical Dictionary for Regulatory Activities (MedDRA) system organ class and preferred term.

Confidential Page 7 of 64

Efficacy Analyses:

For comparisons between groups, the primary analysis will be the combined FDY-5301 treated groups compared to placebo. If the difference between the means of pooled treatment group compared to the placebo group is statistically significant, a step-down procedure will be followed to test the individual FDY-5301 doses compared to placebo. The following testing order of doses will be employed:

- 1) FDY-5301 2 mg/kg versus placebo
- 2) FDY-5301 1 mg/kg versus placebo

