10.2.4.2 Secondary Efficacy Analysis

For secondary endpoints, a sequential analysis will be performed. The continuous secondary efficacy endpoints of MRC-SS and worst SOFA score will be analyzed with an ANCOVA model similar to the one described for the primary endpoint of CPAx total score. The secondary endpoint of overall survival at Day 28 will be analyzed using a Kaplan-Meier approach and a log-rank test, similar to the methodology described for the primary endpoint of organ dysfunction total TTR until Day 28.

The pooled treatment groups versus placebo will be analyzed first, followed by a step-down analysis.

The p-values, least-squares means, standard errors, and the 2-tailed 95% confidence intervals for the treatment groups and placebo group will be presented, where appropriate.

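### Within each primary endpoint, testing 1 mg/kg only after 2 mg/kg adds no error control once the pooled test is significant, and it can cost power for 1 mg/kg

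*Combined protocol and SAP*

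**What the plan says.** Section 10.2.4.1 compares the pooled FDY-5301 arms with placebo on CPAx. If that comparison is significant, "a step-down procedure will be followed to test the individual FDY-5301 doses compared to placebo. The following testing order of doses will be used", and the list puts 2 mg/kg first and 1 mg/kg second. For TTR the same section says "The pooled versus placebo and then step-down analysis procedure will be used". The synopsis (Statistical Methods) repeats the scheme: "The following testing order of doses will be employed". Section 10.2.4.2 carries it to the secondary endpoints: "The pooled treatment groups versus placebo will be analyzed first, followed by a step-down analysis".

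Each primary endpoint is tested at 0.05. Section 10.2.7 says "using a 2-sided significance level of 0.05" for CPAx and "a 2-sided log-rank test at a significance level of 0.05" for TTR. Section 10.2.4.1 also requires both co-primary endpoints to be significant before superiority is concluded. It does not say whether a claim for a single dose must meet that requirement too.

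No sentence states what happens to 1 mg/kg when 2 mg/kg fails. Section 10 leaves further detail to a separate SAP, whose text is not in the document reviewed here.

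**The concern.** An ordered step-down normally means that testing stops at the first failure. Read that way, 1 mg/kg gets no formal conclusion on an endpoint when 2 mg/kg narrowly misses, even if the pooled and the 1 mg/kg comparisons are both significant.

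Such a restriction is worth its price when it is needed to control error. Within one endpoint it is not needed. There are two dose hypotheses, and their only intersection is that neither dose differs from placebo. The pooled comparison is a valid 0.05 test of that intersection. By closed testing, once it rejects, each dose can be tested at the full 0.05 in any order. The parallel rule keeps every rejection that the ordered rule makes and adds some for 1 mg/kg. The chance for 2 mg/kg is the same under both rules.

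At stake is what a trial that puts a third of its subjects on 1 mg/kg can formally conclude about that dose.

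**Working it through.** **Inputs (Section 10.2.7).** Allocation is 1:1:1 ("i.e. 84 subjects per group"), "with a drop-out rate of 15%, corresponding to 213 evaluable subjects". An equal split gives 213/3 = 71 per arm (my assumption). CPAx: SD 12, difference 6. TTR: medians 7 and 4.9 days, ratio 0.70, 213 events, so 71 per arm. The plan gives one effect for the pooled group and none per dose. I start from equal effects and then vary them.

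**The plan's own figures.**
- CPAx, pooled (142 vs 71): SE = 12 × √(1/142 + 1/71) = 1.744; z = 6/1.744 = 3.44; power = Φ(3.44 − 1.96) = 93%. The plan says above 90%.
- TTR, pooled: z = √(213 × 2/9) × ln(1/0.70) = 6.880 × 0.3567 = 2.454; power = Φ(2.454 − 1.96) = 69%. The plan says approximately 70%.

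Both reproduce.

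**Single-dose tests.** Each compares 71 with 71.
- CPAx: SE = 12 × √(2/71) = 2.014; z = 6/2.014 = 2.98; power 85% taken alone.
- TTR: z = √(142/4) × 0.3567 = 2.125; power 57% taken alone.

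**Joint behaviour.** Let z1 and z2 be the statistics for 1 and 2 mg/kg. They share the placebo arm, so their correlation is 0.5, and the pooled statistic is (z1 + z2)/√3.
- Ordered rule for 1 mg/kg: pooled, 2 mg/kg and 1 mg/kg all significant.
- Parallel rule for 1 mg/kg: pooled and 1 mg/kg significant.

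Example on CPAx: observed differences of 5.0 (1 mg/kg) and 3.5 (2 mg/kg) give z1 = 5.0/2.014 = 2.48, z2 = 3.5/2.014 = 1.74 and pooled z = 4.25/1.744 = 2.44. The pooled and 1 mg/kg tests are significant and 2 mg/kg is not, so the order blocks 1 mg/kg.

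**Chance of a conclusion for 1 mg/kg** (normal approximation, 2,000,000 draws, 71 per arm):

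| Effect of 1 mg/kg and 2 mg/kg | Parallel | Ordered | Loss (points) |
|---|---|---|---|
| CPAx 6 and 6 | 83.7% | 75.2% | 8.5 |
| CPAx 5 and 6 | 69.3% | 63.9% | 5.4 |
| CPAx 5 and 7 | 69.8% | 67.9% | 1.8 |
| CPAx 6 and 8 | 84.6% | 83.7% | 0.9 |
| CPAx 4 and 8 | 51.0% | 50.8% | 0.2 |
| CPAx 6 and 5 | 81.8% | 63.9% | 17.9 |
| CPAx 6 and 4 | 77.9% | 47.9% | 30.0 |
| TTR ratio 0.70 and 0.70 | 53.4% | 40.1% | 13.3 |
| TTR ratio 0.75 and 0.65 | 39.6% | 35.6% | 4.0 |
| TTR ratio 0.80 and 0.60 | 26.3% | 25.7% | 0.7 |
| TTR ratio 0.70 and 0.80 | 45.4% | 21.3% | 24.1 |

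Losses were computed before rounding. With all 84 per arm evaluable and equal effects, the losses are 6.3 points (CPAx) and 12.9 points (TTR).

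**Error of the parallel rule within one endpoint (two-sided).** The chance of any false dose conclusion is 0.044 with both doses null, 0.025 with one null and the other at +6, and 0.050 with one null and the other very large. It never exceeds 0.05.

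**Error when a dose claim needs both co-primaries.** Take 1 mg/kg null on CPAx only and 2 mg/kg null on TTR only, with very large effects elsewhere. Both pooled tests then reject almost surely. Without the order, each dose has a 0.05 chance of a false claim. With independent endpoints the chance of at least one is 1 − 0.95² = 0.0975. With the order, 2 mg/kg must pass first, and the rate stays at 0.05.

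**The case against.** **The order can do real work.** If the both-endpoints rule for superiority also applies to single doses, the pooled tests do not protect the dose claims, and dropping the order can nearly double the worst-case error. This stands. The worst case is extreme, and at effects of planning size the rates are low (about 0.02 or less in parallel and 0.01 in order). Strong control must still cover it, so the order should stay for such claims.

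**The size depends on the dose response.** A reader might infer that 8 to 13 points is a minimum loss. It is not: those figures need equal dose effects. Section 1.3 reports that earlier infarction data pointed to 2 mg/kg in particular. If 2 mg/kg is stronger here, the loss was between 0.2 and 5.4 points in the cases run. This stands as a limit on size. The loss is never negative.

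**The plan does not forbid reporting 1 mg/kg.** A reader might infer that nothing could be said about 1 mg/kg after a failed 2 mg/kg test. The text does not support that. The stop is inferred, and Section 10.2.4.1 has estimates and confidence intervals presented for the treatment groups. Only the formal conclusion is affected.

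**High-to-low testing is a legitimate choice.** It is prespecified and controls error. A finding for the lower dose alone may be hard to interpret, and no dose-level power is promised. This stands against calling the order an error. It does not show that the order is needed within an endpoint.

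**Conclusion.** The point holds as an efficiency gain for dose tests on each primary endpoint taken separately. There the order adds no familywise error control. Under equal planned effects and 71 evaluable subjects (or events) per arm, it costs 1 mg/kg 8.5 points on CPAx and 13.3 on TTR. The cost is near 0 to 5 points if 2 mg/kg is stronger. It is about 18 to 30 points on CPAx if 2 mg/kg is weaker by 1 to 2 points.

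These figures rest on a normal approximation, an equal split of evaluable subjects, no TTR censoring (as the plan assumes), and the usual reading that a failed 2 mg/kg test ends the sequence.

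A reader might infer that the order is a mistake and should go everywhere. The documents do not support that. The order is valid and conservative, and it protects a claim that needs both co-primaries. Section 10.2.4.2 also adds a sequence across three secondary endpoints, for which neither error nor power was checked here.

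**What to change.** In Section 10.2.4.1, the synopsis and the SAP:

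1. For each primary endpoint, state that if pooled versus placebo is significant, 2 mg/kg and 1 mg/kg are each compared with placebo at two-sided 0.05 for that endpoint (closed testing), and that error control applies within the endpoint.
2. State whether a claim for a dose requires both co-primary endpoints. For any such claim, keep the order 2 mg/kg then 1 mg/kg, and say in words that a failure at 2 mg/kg ends the sequence.
3. Leave Section 10.2.4.2 as it is unless error control for the combined sequence of endpoints and doses has been checked.

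The cost is a few sentences, made before unblinding. It needs no extra subjects or data and takes nothing from 2 mg/kg. The remaining drawback is interpretive: the trial could report a significant result for 1 mg/kg on one endpoint without one for 2 mg/kg.

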2 TRIAL OBJECTIVES AND ENDPOINTS

The purpose of the trial is to evaluate the efficacy, safety, and PK of FDY-5301 compared to placebo in major trauma ICU patients at risk of ICUAW.

Objectives	Endpoints								
Primary	Coprimary								
To assess the effect of FDY-5301 on muscle function and organ dysfunction in the major trauma ICU population	 Chelsea Critical Care Physical Assessment Tool (CPAx) total score at Day 10, or hospital discharge, whichever occurs first Organ dysfunction total time to recovery (TTR) until Day 28 								
Secondary	Secondary								
To assess the effects of FDY-5301 on other clinical outcomes in the major trauma ICU population	The secondary endpoints will be analyzed in the following sequence: • Medical Research Council Sum Score (MRC-SS) at Day 28 or hospital discharge, whichever occurs first • Worst Sequential Organ Failure Assessment (SOFA) score during ICU stay • Overall Survival at Day 28								
Safety	Safety								
To investigate the safety and tolerability of up to 7 daily bolus IV doses of FDY-5301 in the major trauma ICU population	Safety will be evaluated based on occurrence of or changes throughout the study in the following parameters: • Adverse events (AEs), treatment-emergent adverse events (TEAEs) and serious adverse events (SAEs) • Clinical laboratory assessments (hematology, clinical chemistry, and thyroid function tests) • 12-lead electrocardiogram (ECG) assessments								
Exploratory	Exploratory								
To assess the effects of FDY-5301 on skeletal muscle, muscle function, and other clinical outcomes and to investigate the PK of up to 7 daily bolus IV doses in the major trauma ICU population	 Overall survival at Month 3 and Month 6 from date of injury Time to successful ventilator extubation from time of first dose Time to hospital discharge from first hospital arrival time and time of first dose, and discharge disposition (e.g., home, home with community support, rehabilitation unit, or nursing home) 								

Confidential Page 22 of 64

- Incidence of sepsis through Day 28
- SOFA score and sub score components at Days 1, 3, 7, 14, 21, and Day 28 or ICU discharge, whichever occurs first
- CPAx total score and sub score components at Days 1, 3, 7, 10 (sub score components only), 14, 21, and Day 28 or hospital discharge, whichever occurs first

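### The TTR co-primary, which limits trial success, is tested by a valid log-rank test that makes no use of organ status at first dose; stratifying on that status would be a cheap gain in power.

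*Combined protocol and SAP*

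**What the plan says.** Section 10.2.4.1 (and the synopsis) names two co-primary endpoints, each tested at 0.05, and both must be significant.

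- **TTR.** "The Kaplan-Meier curves will be plotted and the time to recovery will be compared using log-rank test at significance level 0.05". No covariate or stratum is named, not even the randomization stratum. The comparison is pooled active against placebo, then 2 mg/kg and 1 mg/kg in turn.
- **CPAx.** The ANCOVA includes the fracture stratum and takes baseline "CPAx (the first available datapoint) as a continuous covariate".
- **Power (Section 10.2.7).** For TTR, "the study would have approximately 70% power if at least 213 events are observed", assuming an "expected relative risk reduction of 30% and a 2-sided log-rank test at a significance level of 0.05". CPAx is planned at more than 90%.
- **Data at first dose.** Section 2 lists "SOFA score and sub score components at Days 1, 3, 7, 14, 21" among the exploratory endpoints. Table 1 schedules SOFA and organ dysfunction TTR status on Day 1, and safety laboratory tests at screening.
- **Definition of recovery (Section 6.1.3, Appendix 4).** The first day on which cardiovascular, hematologic, hepatic, renal and respiratory criteria are all met, with no failure afterwards.

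**The concern.** The two co-primaries are handled differently. CPAx uses its own starting value; TTR uses nothing measured at the start. Yet the link between starting status and TTR is partly mechanical. Section 10.2.4.1 counts TTR from treatment start plus 1 day, so a subject who meets all five criteria on Day 1 and never fails again has a TTR of 1. A subject on vasopressors and dialysis at that point cannot.

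Eligibility does not make starting status uniform. Shock is judged before arrival or within an hour of it, dosing may begin up to 48 hours after arrival, and no inclusion criterion concerns platelets, bilirubin or creatinine. Section 1.4 itself acknowledges a heterogeneous population. The fracture stratum does not measure organ function.

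What is at stake is efficiency on the endpoint that decides whether the trial succeeds. If starting status is prognostic, leaving it out keeps explainable variation in the comparison.

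**Working it through.** **Inputs (Section 10.2.7).** Placebo: "median expected organ dysfunction recovery time is 7 days for the placebo group". Active: "the median expected organ dysfunction recovery time is 4.9 days for the pooled treatment group". Ratio 4.9/7 = 0.70. There are 213 evaluable subjects; 1:1:1 allocation gives 142 pooled active and 71 placebo.

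**Reproducing the plan's power**

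- TTR (Schoenfeld): Φ(√(213 × 1/3 × 2/3) × |ln 0.70| − 1.96) = Φ(6.880 × 0.3567 − 1.96) = Φ(0.494) = 68.9%. This agrees with the stated 70%.
- CPAx: Φ(6 / (12 × √(1/71 + 1/142)) − 1.96) = Φ(3.440 − 1.96) = Φ(1.480) = 93.1%. This agrees with >90%.
- Both: 0.931 × 0.689 = 64% if independent, and at most 69%. TTR is the limiting endpoint.
- Events for 80% power on TTR: (1.96 + 0.8416)² / (2/9 × 0.3567²) = 278, more than the 252 subjects randomized. Full follow-up of the planned sample would not reach it.
- With exponential recovery, the number recovered by Day 28 is 71 × (1 − 0.5^4) + 142 × (1 − 0.5^(28/4.9)) = 206, which gives 67%. This is the level to expect from the unadjusted test in the simulations.

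**Effect of stratifying.** The documents give no correlation between starting organ dysfunction and TTR, so it is assumed over a range. The simulation uses exponential TTR with the planned medians, 71 against 142 subjects, censoring at Day 28, and a baseline score linked to TTR by a Gaussian copula. The unadjusted log-rank test is compared with one stratified by baseline tertile, with 4,000 runs per row (simulation error √(0.66 × 0.34/4000) = 0.7 points per figure).

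| Assumed correlation | Continuous time: unadjusted → stratified | Whole days: unadjusted → stratified |
|---|---|---|
| 0 | not tabulated | 66% → 64% |
| 0.3 | 67% → 67% | 67% → 69% |
| 0.4 | 65% → 69% | 68% → 71% |
| 0.5 | 66% → 72% | 66% → 73% |
| 0.6 | 66% → 76% | 67% → 77% |

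A further whole-day simulation gave 64% → 66% at 0.3 and 66% → 74% at 0.5. A smaller one (1,200 runs) gave 65% → 67% and 66% → 71%. Five strata instead of three gave 74% at 0.5, 78% at 0.6 and 63% at zero. Type I error of the stratified test was 4.6 to 5.0%.

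**A different model.** Prognostic strength is expressed as log-hazard per SD of baseline severity. With the marginal ratio held at 0.70, unadjusted → stratified power is 67% → 69% at 0.25 and 66% → 75% at 0.50; at zero it is 67% → 66%. If the planned medians are kept, so that the ratio within severity levels is 0.70, then at 0.50 it is 52% → 61%. Stratifying still wins there, but neither test reaches the planned 70%.

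**Cox alternative.** A Cox model with the score as a linear covariate shows more power (66% → 77% at correlation 0.5 in continuous time). Its type I error is in doubt: one set of whole-day runs gave 4.2 to 5.2%, but others with Efron ties and the model-based Wald test gave about 6 to 7% at correlations of 0.4 to 0.5. Part of its apparent advantage may therefore come from a test that runs above its level.

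**The case against.** An unadjusted log-rank test in a randomized trial is valid. It holds its error rate, needs no covariate model, and is the test on which the sample size was based. Chance imbalance is already covered by the 5% level. That a marginal hazard ratio lies nearer 1 than a conditional one is non-collapsibility, not bias. All of this stands. A reader might infer that the TTR analysis or its power statement is wrong; the documents do not support that.

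The size of the gain is assumed. There are reasons in the protocol to expect a modest correlation: Section 4.1 requires shock and anticipated ventilation, which narrows the range in two systems, and later complications can reset TTR because any subsequent failure counts. At 0.2 the smaller simulation showed a loss (65% → 63%). The simulations also leave out death before recovery, which could move the gain either way. These points stand, and they are why the result is given as a range.

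It is also tempting to treat Day 1 SOFA as the baseline of this outcome. That does not hold. The Day 1 window is 24 hours either side of first dose, SOFA takes the worst value of the day (Section 6.1.4), and its cut-offs differ from Appendix 4 (for example platelets 150 and 100 against 120, in thousands; mean arterial pressure 70 against 60). The covariate must be built from pre-dose values on the Appendix 4 criteria.

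Finally, Section 10 defers detail to a separate SAP, so it cannot be said that starting status enters no TTR analysis at all. The primary test, however, is fixed in Section 10.2.4.1.

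**Conclusion.** The point holds as a cheap improvement. The limiting co-primary is tested validly but without information that is largely collected already and is likely to be prognostic. Stratifying the log-rank test gains about 0 to 2 points of power at a correlation of 0.3, 3 to 4 at 0.4, 6 to 8 at 0.5 (5 in the smallest simulation) and about 10 at 0.6. It loses about 1 to 3 points at zero. If the endpoints are independent, about 93% of any TTR gain carries into the chance that both succeed: 6 to 8 points becomes 0.931 × 6 = 5.6 to 0.931 × 8 = 7.4.

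These figures rest on the planned medians, exponential recovery, no deaths, and a correlation that the documents do not supply. A reader might infer that 11 points are being lost, from the Cox figure at 0.5. That rests on an assumed correlation, continuous time and a test whose level is uncertain, so it should not be relied on.

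**What to change.** In Section 10.2.4.1 and the synopsis, before unblinding:

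1. Make the primary TTR test a log-rank test stratified by the number of Appendix 4 systems not meeting recovery criteria at the last assessment before first dose, in pre-set categories (for example three).
2. Use pre-dose values only: screening laboratory tests for platelets, bilirubin and creatinine; pre-dose chart values for the cardiovascular, ventilation and dialysis elements.
3. Assign subjects with missing status to a stratum by a rule that ignores treatment arm, so that none is dropped.
4. Use the same test for the 2 mg/kg and 1 mg/kg step-down comparisons.
5. Keep the Kaplan-Meier curves and the unadjusted log-rank test as supportive. Use a Cox model only as supportive, or with a robust variance.
6. Report any stratified hazard ratio, which is conditional on starting status, beside the unadjusted one.

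The cost is protocol and SAP wording, some chart abstraction (possibly extra CRF fields) where Day 1 was scored after dosing, and about 1 to 3 points of power if starting status turns out not to predict recovery. No subjects or visits are added.
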